**CONFIDENTIAL**

212171 (RSV MAT-009)  
Protocol Amendment 5 Final

Visit / Contact	Screening	V1	V2*	Contacts (Monthly)	V3	V4	C1	Event Driven			
Gestational Age (GA)	≤ 28 days before V1	24 0/7 – 34 0/7		Until Delivery	Delivery			Additional contact(s) 	Safety visit	MA-RTI visit	For monthly contacts: Section 8.2.1.2.2. Additional contact(s) and/or safety visit(s) can be made between Visit-2 and the Delivery visit, if deemed necessary.
Visit Day	D-28 – D1 before randomization	D1	D31		D1PD	D43 PD	D181 PD	V2-Delivery			Table 3
Train maternal participant /LAR on use of electronic diary		O Stage A									Section 10.3.8
Distribute electronic diary to maternal participant / LAR.		O Stage A									Section 8.3.1
Review electronic diary entries			O Stage A								
Return electronic diary			O Stage A								
Concomitant medications / vaccinations		•	•	•	•	•	•	•	•	•	Sections 6.5.1 and 6.5.3
All unsolicited AEs (Days 1 to 30)		•	•						•	•	Sections 8.3.1, 10.3.4 and 10.3.8
Pregnancy-related AESIs		•	•	•	•	•	•	•	•		Table 4, Sections 8.3.1, 8.3.3, 8.3.4, and 10.3.5. Must submit an Expedited AE report.
MAEs other than MA-RTIs		•	•	•	•	•		•	•		Medically attended RTIs to be reported up to C1.
MA-RTI signs										•	Sections 8.3.1, 8.3.3, 8.4 Note: As from protocol amendment 4 nasal swab

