**CONFIDENTIAL**

212171 (RSV MAT-009)  
Protocol Amendment 5 Final

Visit / Contact	Screening	V1	V2*	Contacts (Monthly)	V3	V4	C1	Event Driven			
Gestational Age (GA)	≤ 28 days before V1	24 0/7 – 34 0/7		Until Delivery	Delivery			Additional contact(s) 	Safety visit	MA-RTI visit	For monthly contacts: Section 8.2.1.2.2. Additional contact(s) and/or safety visit(s) can be made between Visit-2 and the Delivery visit, if deemed necessary.
Visit Day	D-28 – D1 before randomization	D1	D31		D1PD	D43 PD	D181 PD	V2-Delivery			Table 3
											from maternal participants will no longer be collected and MA-RTI visit is no longer required.
SAEs, MA-RTI associated AEs and AEs leading to study withdrawal		•	•	•	•	•	•	•	•	•	Sections 7.2, 8.3.1 and 10.3.8
SAEs related to study participation or concurrent GSK medication/vaccine	•	•									Sections 8.3.1 and 10.3.8
Subsequent pregnancies						•	•		•	•	Sections 8.3.1 and 10.3.8
Record interest in joining future extension study	○						•				Section 6.7
Screening conclusion	•										
Study conclusion							•				Section 4.4
Investigator sign-off at study conclusion							•				

The timing of an event-driven site visit (e.g., to further evaluate a potential AE or MA-RTI) cannot be defined with precision in the protocol. Event-driven visits may occur throughout the study. • is used to indicate a study procedure that requires documentation in the individual eCRF. ○ is used to indicate a study procedure that does not require documentation in the individual eCRF. V = visit; D = day; GA = gestational age; MA-RTI = medically attended respiratory tract illness; PD = post delivery.

\* V2 may be replaced by V3, depending on delivery date.

 In addition to the monthly contacts between Visit-2 and the Delivery visit, additional not pre-specified visits and contacts (any desired frequency) can be made between Visit-2 and the Delivery visit, as per investigator's or maternal participant's discretion.

CONFIDENTIAL

212171 (RSV MAT-009)  
Protocol Amendment 5 Final

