**Table 3 Intervals between study visits and contacts**

Interval	Optimal interval in Days	Allowed interval in Days	Additional Information
Maternal participants			
Screening to V1	0	0– 28	The screening interval extends from Day -28 to Day 1 before randomization. If all eligibility criteria can be confirmed on the day of screening and all required procedures can be performed, then, “Screening” and “Visit 1” may occur on the same day (refer to Section 8.2.1.2).  Data from all screening procedures must be available and eligibility must be confirmed before the participant is randomized.  If a participant is screened but not vaccinated within the allowed interval, a re-screening should be done to establish the participant’s eligibility. Please make sure the participant’s gestational age is still within the allowed range, refer to Section 10.8 for guidance on gestational age assessment.
V1 to V2	30	20 - 45	If this visit occurs before Day 25, the site must contact the participant to collect information about any additional unsolicited adverse events that may occur between the date of the visit and Day 31.
Monthly contacts	~ every 25 – 35		Monthly beginning after Visit 2 until Delivery. Contacts are additional to and do not replace protocol specified Visits. Additional contact(s)/visit(s) can be made more often if deemed necessary by the investigator or the maternal participant.
V3 (delivery)	0	1 day before to 3 days after delivery	For maternal participants in the Stage A immunogenicity sub-cohort: collect maternal blood sample at any point from the start of labor up to delivery. (NOTE: For participants for which a cesarean section is planned, the sample may be collected as soon as the participant arrives at the clinic and the intravenous line is inserted to prepare them for the cesarean section). If blood is not collected during delivery, collect maternal blood sample no later than 72 hours after delivery. For all participants in both Stage A and Stage B: A cord blood sample should be collected at the time of delivery. If cord blood cannot be collected at delivery, a blood sample should be collected from the infant participant as soon as possible and no later than 72 hours after birth.
V3 to V4	42	30 – 60	If this visit occurs before Day 43, the site must contact the participant to collect information about any additional AESIs that may have been identified or may have occurred between the date of the visit and Day 43.
V3 to C1	180	165 – 200	

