To evaluate the safety of a single IM dose of the RSV Maternal vaccine in all maternal participants, from Visit 1 up to 6 months after delivery.	Occurrence of serious adverse events (SAEs)  , AEs leading to study termination, and medically attended RTIs in all maternal participants from Visit 1 (Day 1) up to 6 months after delivery.  Occurrence of all other medically attended AEs in all maternal participants from Visit 1 (Day 1) up to Day 42 after delivery.

Secondary safety objectives	Secondary safety endpoints

To evaluate pregnancy outcomes and pregnancy-related adverse events of special interest after a single IM dose of the RSV Maternal vaccine administered to maternal participants, from Visit 1 up to 6 weeks after delivery (Visit 4).
	
Pregnancy outcomes from Day 1 (Visit 1) up to 6 weeks after delivery (Day 43 post-delivery, Visit 4). These include live birth with no congenital anomalies, live birth with minor congenital anomaly(ies) only; live birth with at least one major congenital anomaly, fetal death/still birth (antepartum or intrapartum) with no congenital anomalies, fetal death/still birth (antepartum or intrapartum) with only minor congenital anomalies, fetal death/still birth (antepartum or intrapartum) with at least 1 major congenital anomaly; elective/therapeutic termination with no congenital anomalies; elective/therapeutic termination with only minor congenital anomalies, and elective/therapeutic termination with at least 1 major congenital anomaly.
 
Pregnancy-related adverse events (AEs) of special interest from Day 1 (Visit 1) up to 6 weeks after delivery (Day 43 post-delivery, Visit 4). These include maternal death, hypertensive disorders of pregnancy (gestational hypertension, pre-eclampsia, pre-eclampsia with severe features including eclampsia), fetal growth restriction, pathways to preterm birth (premature preterm rupture of membranes, preterm labor, provider-initiated preterm birth), gestational diabetes mellitus, chorioamnionitis.

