##### 6.5.1. Maternal participants

- **All folate and iron supplements** beginning the month before the estimated date of conception and continuing through delivery (i.e., through Visit 3). These supplements should be reported when taken independently and/or when included in a multivitamin mineral supplement.

- All antibiotics, antivirals, analgesics and anti-pyretics taken within 7 days before dose administration.
- All concomitant **vaccines** beginning the month before the estimated date of conception and throughout the study (i.e., through Contact 1).
- **Prophylactic medication** related to the effects (actual or anticipated) of study vaccine/product administration (e.g., medication administered either in the absence of ANY symptom and in anticipation of a reaction to the study vaccine, or to prevent re-occurrence of one or more post-vaccination AEs such as headache).
- Any concomitant **medications/products** given for pre-existing medical conditions, beginning at Visit 1 and ending at Contact 1 (Day 1 to Day 181).
- Any concomitant **medications/products** associated with a solicited event or with an unsolicited adverse event, beginning at Visit 1 and ending at Visit 2 (Day 1 to Day 31).
- Any **corticosteroids for fetal lung maturation** administered prior to/during labour or delivery, as well as any **antibiotics** administered in the last week prior to delivery and/or during labor. Note: Standard of care medications/products administered routinely during labor/delivery (e.g., General/regional/local anesthetics, analgesics, etc) do not need to be reported.
- Any concomitant **medications/products** associated with a medically attended adverse event (MAE) other than an MA-RTI beginning at Visit 1 and ending at Visit 4 (Day 1 to Day 43 post delivery).
- Any concomitant **medications/products** associated with an MA-RTI beginning at Visit 1 and ending at Contact 1 (Day 1 to Day 181 post delivery).

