**9.4. Statistical analyses****9.4.1. General considerations (Amended 23 February 2023)**

The statistical analysis plan (SAP) will be finalized before database lock and will include a more technical and detailed description of the statistical analyses to be performed. This section summarizes planned statistical analyses of primary and secondary endpoints.

If, during the trial, changes need to be made on primary objectives and statistical methods related to those objectives, the protocol will be amended. Changes on *secondary*/tertiary

objectives, along with the reason(s) for the changes, will be documented in the SAP and the Clinical Study Report.

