
Pregnancy outcomes from Day 1 (Visit 1) up to 6 weeks after delivery (Day 43 post-delivery, Visit 4). These include live birth with no congenital anomalies, live birth with minor congenital anomaly(ies) only; live birth with at least one major congenital anomaly, fetal death/still birth (antepartum or intrapartum) with no congenital anomalies, fetal death/still birth (antepartum or intrapartum) with minor congenital anomalies only, fetal death/still birth (antepartum or intrapartum) with at least 1 major congenital anomaly; elective/therapeutic termination with no congenital anomalies; elective/therapeutic termination with minor congenital anomalies only, and elective/therapeutic termination with at least 1 major congenital anomaly.
	

Pregnancy-related adverse events (AEs) of special interest from Day 1 (Visit 1) up to 6 weeks after delivery (Day 43 post-delivery, Visit 4). These include maternal death, hypertensive disorders of pregnancy (gestational hypertension, pre-eclampsia, pre-eclampsia with severe features including eclampsia), fetal growth restriction, pathways to preterm birth (premature preterm rupture of membranes, preterm labor, provider-initiated preterm birth), gestational diabetes mellitus, chorioamnionitis.
	

Occurrence of serious adverse events (SAEs), AEs leading to study termination, and medically attended AEs in all maternal participants from Visit 1 (Day 1) up to 6 months after delivery.
	

Secondary Safety Endpoints – Infant Participants
	

The occurrence of neonatal AEs of special interest (reported up to 6 weeks after birth). These include small for gestational age, low birth weight including very low and extremely low birth weight (<2500 g, <1500g, <1000g), congenital anomalies (major external structural defects, internal structural defects, functional defects), neonatal death (in an extremely pre-term birth ($22 \leq GA < 28$ weeks), in a preterm live birth ($28 \leq GA < 37$ weeks), or in a term live birth), preterm birth.
	

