7. CONDUCT OF ANALYSES

7.1. Sequence of analyses

An interim analysis of safety endpoints for both maternal and infant participants has been performed, with the focus on demonstrating the safety profile at Day 43 post-delivery. The interim analysis was deemed necessary following the identification of the safety signals documented in protocol amendment 4, which assisted in the better characterization of the safety information including the signals. The interim analysis was performed after all infants completed the 43 days post-delivery timepoint. The safety endpoints are identical to those listed in section 2, and the statistical analysis methods are similar to section 5.4.1. with minor modifications. In addition, summaries of demographics, participant disposition, concomitant medication/vaccinations and medical history was included. This analysis was performed by an external Independent Data Analysis Center (IDAC). In addition, monthly safety analyses are conducted, where most of the analyses have been generated by IDAC and monitored by the SRT on a monthly basis and by an Independent Data Monitoring Committee (IDMC) on a bi-monthly basis. Additional non-standardized ad-hoc analyses (safety signal deep dive) are performed by internal GSK.

6 Month Post-delivery interim analysis occurred as described below:

- When all maternal and infant participants enrolled completed 6 months follow-up post-delivery/birth (to evaluate primary and secondary efficacy endpoints, reactogenicity and safety)

Final analysis will occur as described below:

- When all infant participants have completed Visit 5-NB (month 12, LSLV), a final safety analysis (for all maternal and infant participants in both Stage A and Stage B), a final secondary efficacy analysis up to 12 months follow up post birth, and a final immunogenicity analysis will be performed. Analyses of any evaluated tertiary endpoints may also be performed.

6 Month Post-delivery interim analysis was performed by internal GSK, so will be the final analysis.

If the data for tertiary endpoints becomes available at a later stage, (an) additional analysis/analyses will be performed.

Description	Disclosure Purpose
Day 43 post-delivery interim analysis	Internal
6 Month post-delivery interim analysis	Public Disclosure.
Final Analysis at Month 12 post birth	Public Disclosure, Study Report

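### SAP 5.4.1 runs all maternal medically attended AEs to 6 months after delivery, while the endpoint tables and the collection schedule end the non-respiratory ones at about Day 42

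*SAP*

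**What the plan says.** **Analysis text.** SAP 5.4.1 has a single maternal row covering SAEs, AEs causing study termination, and "medically attended AEs in all maternal participants from Visit 1 (Day 1) up to 6 months after delivery". Protocol 9.4.4.4 uses the same wording. Neither separates respiratory from other events.

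**Endpoint tables.** SAP Table 1 and protocol Table 4 split the endpoint. SAEs, AEs causing termination and medically attended RTIs run to 6 months after delivery. The next line reads "Occurrence of all other medically attended AEs in all maternal participants from Visit 1 (Day 1) up to Day 42 after delivery".

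**Collection.** In protocol Table 1, the row for MAEs other than medically attended RTIs is marked at Visits 1 to 4, the monthly contacts, the additional contacts before delivery, and safety visits. It is blank at Contact 1, the 6-month contact. Its comment is "Medically attended RTIs to be reported up to C1". Protocol 6.5.1 records medication "associated with a medically attended adverse event (MAE) other than an MA-RTI beginning at Visit 1 and ending at Visit 4". A footnote to Table 1 adds "Event-driven visits may occur throughout the study".

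**Changes.** SAP section 8 does not list a longer MAE window among the changes from planned analyses.

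**The concern.** One secondary safety endpoint has two analysis windows, in both documents. A programmer who follows SAP 5.4.1 produces a maternal MAE table labelled to 6 months after delivery. Routine collection of non-RTI MAEs ends at Visit 4, so most of the post-delivery part of that label has no scheduled data behind it.

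If the row is read as a 6-month incidence, the non-RTI result is too low by an unknown amount. If it is a simple percentage of women, it is close to the Day 42 result, with a few later events added and the wrong label. The percentage is the likelier reading, because the only within-group method visible in the SAP is an exact interval for a proportion (SAP 10.1.4.1).

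The trial stopped enrolment because of a safety signal, and SAP 7.1 marks its 6-month interim for public disclosure. The period that a maternal safety table covers should therefore be stated correctly.

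**Working it through.** **1. The texts side by side**

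| Source | RTI-related MAEs | Other MAEs |
|---|---|---|
| SAP Table 1, protocol Table 4 | 6 months | Day 42 |
| SAP 5.4.1, protocol 9.4.4.4 | 6 months | 6 months (merged row) |
| Protocol Table 1 (schedule) | Contact 1 | Visit 4, then safety visits only |
| Protocol 6.5.1 (medication) | Contact 1 | Visit 4 |

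The schedule and the medication rule both agree with the endpoint tables. The schedule row for pregnancy-related AESIs does carry a mark at Contact 1, so the blank for non-RTI MAEs looks deliberate.

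**2. Post-delivery days without scheduled collection.** Protocol Table 3 puts Visit 4 at 42 days after delivery (allowed 30 to 60) and Contact 1 at 180 days (allowed 165 to 200).

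- Target schedule: 180 − 42 = 138 days; 138/180 = 76.7% of the post-delivery period.
- Shortest gap: 165 − 60 = 105 days; 105/165 = 63.6%.
- Longest gap: 200 − 30 = 170 days; 170/200 = 85.0%.

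**3. Share of the row's full window.** The row starts at Visit 1, so time before delivery belongs in the denominator. Vaccination is allowed at 24 to 34 weeks. The documents give no typical gestational age at delivery, so 40 weeks is assumed.

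- Vaccinated at 24 weeks: (40 − 24) × 7 = 112 days; 112 + 180 = 292; 138/292 = 47.3%.
- Vaccinated at 34 weeks: (40 − 34) × 7 = 42 days; 42 + 180 = 222; 138/222 = 62.2%.

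With delivery at 37 weeks, the protocol's boundary of term, the shares are 138/(91 + 180) = 50.9% and 138/(21 + 180) = 68.7%.

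**4. What is captured after Visit 4.** SAEs and medically attended RTIs continue to Contact 1. Event-driven safety visits can pick up other MAEs at any time. Protocol 10.3.4 asks participants to contact the site about medically attended events. Protocol 10.3.8.3.1 follows MAEs already reported but schedules no collection of new ones. Capture of non-RTI MAEs is therefore unscheduled, not nil. The period bars of protocol Table 18 could not be read in the text available here and should be checked against the laid-out protocol.

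**5. Day count.** With delivery as Day 1, 42 days after delivery is Day 43, the label of Visit 4, so the two labels mark the same target point. SAP 10.1.2.10, however, counts maternal onset from vaccination. When Visit 4 falls before Day 43, protocol Table 3 says "the site must contact the participant to collect information about any additional AESIs that may have been identified or may have occurred"; it does not name MAEs.

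**The case against.** The strongest answer is that this is a drafting slip with little effect. The SAP row reads like the first sentence of the Table 1 endpoint with RTIs changed to AEs and the second sentence lost. SAP 5.4.1 says that it follows the protocol, and its opening text lists MAEs and medically attended RTIs as separate summaries. The method cell is redacted and the table list is a separate document (SAP 10.2), so the split may already be programmed. Collection rules are the same in both groups.

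Much of this stands. It limits the consequence but does not remove the conflict: the visible analysis row still contradicts Table 1, and protocol 9.4.4.4 contradicts protocol Table 4.

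A reader might infer more than the documents support:

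- **That 77% of events are missed.** The figure is a share of post-delivery days. The documents give no MAE counts or rates over time.
- **That the comparison between groups is biased.** Site staff and mothers were unblinded (protocol 6.3.6), so later voluntary reporting could differ by group. Nothing in the documents shows that it did.
- **That the 6-month interim tables are wrong.** SAP 7.1 does not say which window they used. For the Day 43 interim it says "The safety endpoints are identical to those listed in section 2", and that section has the split.
- **That maternal vaccine efficacy is distorted.** The RSV-associated RTI endpoint keeps a label to Contact 1, although maternal swabbing stopped. Protocol 2.1 already limits that assessment to cases swabbed before enrolment stopped, so the visible gap is one of labelling.

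**Conclusion.** The inconsistency is real and worth fixing before the final analysis. SAP 5.4.1 and protocol 9.4.4.4 carry all maternal MAEs to 6 months after delivery, against a Day 42 limit for non-RTI events in both endpoint tables, the visit schedule and the medication rule. Followed as written, the row gives a mislabelled result of mixed completeness.

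On the target schedule the uncovered stretch is 138 of 180 post-delivery days. From Visit 1 it is about 47% to 62% of the window if delivery is at 40 weeks. The effect on any reported percentage cannot be estimated from the documents. Confidence is high for the conflict in the text. It is lower for the consequence, because the method cell is redacted and the Table 18 bars could not be checked. The primary endpoints are not affected.

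**What to change.** - Split the row in SAP 5.4.1, and in protocol 9.4.4.4 if the protocol is amended, to match SAP Table 1: (i) SAEs, AEs causing study termination and medically attended RTIs to 6 months after delivery; (ii) all other MAEs with onset up to 42 days after the delivery date.
- State that this count starts at delivery. SAP 10.1.2.10 counts from vaccination, and Visit 4 can fall 30 to 60 days after delivery, so a cut by visit would not give the same events.
- Check which window the 6-month interim maternal MAE tables used. Relabel them only if they used the merged row.
- Minor labelling note: the visible SAP text for RSV-associated maternal RTIs (Table 1 and 5.2.2) does not carry the protocol 2.1 limit. If it is added, use one defined cutoff. Protocol 2.1 refers to the enrolment stop (25 February 2022, protocol 10.6.4), whereas protocol Table 1 ends swabs from Amendment 4 (15 March 2022, protocol 10.11). Say also whether locally tested cases, allowed in SAP 9.2.2, count.

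The cost is low: SAP wording, one divided table and a check of tables already produced. Protocol 9.4.1 says that changes on secondary objectives, "along with the reason(s) for the changes, will be documented in the SAP and the Clinical Study Report", so a separate protocol amendment may not be needed.

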**8.2.2.1. Physical examination at Visits 1-NB through 5-NB**

A physical examination will be performed at each protocol-specified visit (Visits 1-NB through 5-NB).

The examination will include assessment of the following:

- Weight, length, head circumference
- Temperature, heart rate and respiratory rate
- Age-appropriate organ system examination including: eyes, ears, musculoskeletal, reflexes (motor/visual/sound), pulmonary (chest auscultation), cardiovascular, neurological, skin and genitourinary.
- Presence of congenital anomalies.

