**CONFIDENTIAL**

212171 (RSV MAT-009)  
Protocol Amendment 5 Final

Applies to Stage A and Stage B unless otherwise noted below

	Before Delivery*				Delivery/Birth	Post-Delivery/Birth*					
Timepoint	D-28	D1	D7	D31		D 43	D91	D121	D181	M9	M12
Maternal participant visits	Pre-**	V1		V2	V3	V4			C1		
Infant visits					V1-NB	V2-NB	C1-NB	V3-NB	V4-NB	C2-NB	V5-NB
SAEs related to study participation or concurrent GSK medication or vaccine	M										

Pre = pre-vaccination; V=visit; D: Day; M = Maternal participants; I= Infant participants. \* Approximately monthly contacts pre- delivery also occur within the timeframes described above and are described in Section 1.2. \*\*i.e. consent obtained. \*\*\* If subsequent pregnancy occurs during the study, follow-up may extend up to 8 weeks post birth of the infant from that subsequent pregnancy. \*\*\*\*AESIs include adverse pregnancy outcomes, pregnancy related AEs of special interest and neonatal AEs of special interest (for details refer to Section 10.3.5). Neonatal AEs of special interest identified after V2-NB (e.g., congenital anomalies) will continue to be reported as such.

#Due to the stop on study enrollment and vaccination, MA-RTI surveillance of the maternal participants will no longer be performed.

The investigator or designee will record and immediately report all SAEs (including RTIs associated with hospitalization of a maternal or infant participant and all adverse pregnancy outcomes), as well as all pregnancy related AESIs and neonatal AESIs to the sponsor or designee via the Expedited AE Reporting Form. This reporting should, under no circumstances, occur later than 24 hours after the investigator becomes aware of an SAE/AESI, as indicated in Section 10.3.10. and Table 19. The investigator will submit any updated SAE/AESI data to the sponsor within 24 hours of it being available.

A post-study SAE is defined as any event that occurs after the end of the study. Investigators are not obligated to actively seek SAEs from former study participants. However, if the investigator learns of any SAE, including a death, at any time after a participant has been discharged from the study, and he/she considers the event to be reasonably related to the study vaccine/product, the investigator will promptly notify the Study Contact for Reporting SAEs mentioned in the Table 20.

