Level 2 ultrasound (also known as a fetal anomaly ultrasound scan or fetal morphology assessment)	Comprehensive, detailed evaluation of fetal anatomy and development that is usually performed at approximately 20 weeks of gestational age. In addition to standard ultrasound parameters such as fetal heart activity and gestational age estimation, a Level 2 ultrasound usually includes assessment of amniotic fluid levels; assessment of the condition of the placenta, cervix, and uterus; and detection of fetal anomalies.

Local healthcare provider	A healthcare provider who provides participants with medical care per local standards. This individual may or may not be a member of the study staff.
Neonate (or Newborn)	An infant 28 days old or younger.
Neonatal adverse events of special interest	Adverse events that occur from birth through 28 days of age and are to be reported as neonatal AESIs are listed in Table 4 and Section 10.3.5 . It is anticipated that most neonatal AESIs will be identified (and thus may be reported in the eCRF) by or before the Day 43 visit (V2-NB). However, as indicated in Table 18 , any neonatal AESIs identified after V2-NB should also be reported in the eCRF.
Parental concern	The parent(s) / Legally Acceptable Representative(s) are concerned about the infant’s respiratory tract illness (or general health in the context of the respiratory tract illness) and intend to seek medical care
Participant:	Term used throughout the protocol to denote an individual who has been contacted to participate or participates in the clinical study, either as a recipient of the vaccine/product or as a control.  Synonym: subject
Participant number:	A unique identification number assigned to each participant who consents to participate in the study.
Pregnancy related adverse events of special interest	Pregnancy related events that occur up to 42 days after delivery and are to be reported as AESIs are listed in Table 4 and Section 10.3.5 .
Primary completion date:	The date that the final participant was examined or received an intervention for the purpose of final collection of data for all primary outcomes, whether the clinical trial/ pharmacological-epidemiological study was concluded according to the pre-specified protocol or was terminated.

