
To evaluate pregnancy outcomes and pregnancy-related adverse events of special interest after a single IM dose of the RSV Maternal vaccine administered to maternal participants, from Visit 1 up to 6 weeks after delivery (Visit 4).
	
Pregnancy outcomes⁵ from Day 1 (Visit 1) up to 6 weeks after delivery (Day 43 post-delivery, Visit 4). These include live birth with no congenital anomalies, live birth with minor congenital anomaly(ies) only; live birth with at least one major congenital anomaly, fetal death/still birth (antepartum or intrapartum) with no congenital anomalies, fetal death/still birth (antepartum or intrapartum) with only minor congenital anomalies, fetal death/still birth (antepartum or intrapartum) with at least 1 major congenital anomaly; elective/therapeutic termination with no congenital anomalies; elective/therapeutic termination with only minor congenital anomalies, and elective/therapeutic termination with at least 1 major congenital anomaly.
 
Pregnancy-related adverse events (AEs) of special interest from Day 1 (Visit 1) up to 6 weeks after delivery (Day 43 post-delivery, Visit 4). These include maternal death, hypertensive disorders of pregnancy (gestational hypertension, pre-eclampsia, pre-eclampsia with severe features including eclampsia), fetal growth restriction, pathways to preterm birth (premature preterm rupture of membranes, preterm labor, provider-initiated preterm birth), gestational diabetes mellitus, chorioamnionitis.^{4,5}

To evaluate the occurrence of neonatal AEs of special interest (reported up to 6 weeks after birth), in infants born to mothers who were vaccinated with a single IM dose of the RSV Maternal vaccine
	
The occurrence of neonatal AEs of special interest (reported up to 6 weeks after birth). These include small for gestational age, low birth weight including very low and extremely low birth weight (<2500 g, <1500g, <1000g), congenital anomalies (major external structural defects, internal structural defects, functional defects), neonatal death (in an extremely preterm birth [22≤GA<28 weeks], in a preterm live birth [28≤GA<37 weeks], or in a term live birth), preterm birth.^{4,5}

Tertiary objectives:

CCI

¹By “medically assessed” it is meant that the infant was evaluated by a healthcare professional (physician, nurse, etc) for the lower respiratory tract illness.

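### Congenital anomalies identified after 6 weeks are still collected, but as worded they fall outside the neonatal AESI and pregnancy-outcome endpoints, and no visible rule brings them back in

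*SAP*

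**What the plan says.** **Analysis windows.** In SAP 5.4.1 the secondary infant safety endpoint is "The occurrence of neonatal AEs of special interest (reported up to 6 weeks after birth". SAP Table 1 and Protocol Table 4 carry the same limit. The companion maternal endpoint in SAP 5.4.1 is "Pregnancy outcomes from Day 1 (Visit 1) up to 6 weeks after delivery (Day 43 post-delivery, Visit 4". Its categories are sorted by anomaly status: "These include live birth with no congenital anomalies, live birth with minor congenital anomaly(ies) only; live birth with at least one major congenital anomaly", and likewise for stillbirths and terminations.

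**Collection.** The footnote to Protocol Table 18 (section 8.3.1) states: "Neonatal AEs of special interest identified after V2-NB (e.g., congenital anomalies) will continue to be reported as such". The Protocol glossary (10.7.2) says "It is anticipated that most neonatal AESIs will be identified (and thus may be reported in the eCRF) by or before the Day 43 visit", and asks that those identified later also be entered in the eCRF. The notes to Figure 2 in both documents agree. Protocol 8.2.2.1 states "A physical examination will be performed at each protocol-specified visit (Visits 1-NB through 5-NB", and its list of assessments includes "Presence of congenital anomalies".

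**What else covers month 12.** The primary infant safety endpoint counts SAEs, AEs leading to study termination and medically attended AEs to 12 months. The final safety analysis (SAP 7.1) follows completion of Visit 5-NB.

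**The concern.** Congenital anomaly is a named AESI in a trial of exposure during pregnancy. The protocol treats AESI as the class that always captures major anomalies: under 8.3.4.2 they are AESIs whether or not they qualify as SAEs. If an internal or functional defect is first recognised after Visit 2-NB, the site reports it as an AESI, but the AESI endpoint as worded does not take it in. The pregnancy-outcome window has also closed by then.

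The by-arm comparison of congenital anomalies as AESIs would then rest on anomalies found in the first 6 weeks, while the database holds more. The study is fully unblinded (SAP section 8). A counting rule left open now would be settled by people who can see treatment assignment.

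**Working it through.** The plan gives no figure to reproduce. The check compares the windows and then follows one case through the rules.

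**Windows.** Inputs are from Protocol Table 3 (optimal intervals: birth to V2-NB 42 days, birth to V5-NB 365 days; V2-NB allowed at days 30 to 60).
- Follow-up outside the 6-week window: 365 − 42 = 323 days; 323 / 365 = about 88%.
- Infant examinations after Visit 2-NB: V3-NB, V4-NB and V5-NB (Days 121, 181 and 366 in Protocol Table 2), so 3 of 5.
- Latest in-window V2-NB visit: 60 − 42 = 18 days past 6 weeks. An anomaly found at a compliant V2-NB visit could itself miss a strict cut-off.

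**One case: a major anomaly present at birth and first found at V3-NB, about Day 121.**
1. Is it a neonatal AESI? Yes. It was present at birth, so it meets the glossary's period of birth to 28 days, and the Table 18 footnote has it reported as an AESI.
2. Is it in the AESI endpoint? As worded, no: it was not reported by 6 weeks.
3. Does the date rule help? SAP 10.1.2.10 counts infant onset to the start date or the date of diagnosis. Start date gives day 1; diagnosis gives about day 121. Two programmers could place the case differently.
4. Does it change the pregnancy outcome? The endpoint ended at Day 43. A participating infant's anomaly goes in the infant eCRF (footnote to Protocol Table 21). No visible text says whether the outcome category is updated from it.
5. Is it in the 12-month primary infant safety endpoint? Yes, if it is an SAE or medically attended. Congenital anomaly is an SAE criterion (Protocol 10.3.2, item e, applied through 8.3.4.2), and anomalies not on the MACDP list may still be reported as SAEs or medically attended AEs.
6. Is it in the planned listings? SAP section 8 names SAEs, AEs leading to withdrawal, medically attended AEs, adverse pregnancy outcomes and pregnancy-related AESIs. Neonatal AESIs are not named.

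For a minor anomaly the route is thinner. It is never an AESI, and if it is neither an SAE nor medically attended it may sit only on the infant physical-examination page (8.3.4.2). Yet minor anomalies define one of the live-birth categories.

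**Size.** The count would be N × p × f, where p is the share of infants with an anomaly and f the share of those first identified after 6 weeks. N is 5235 (Protocol 2.3: 3496 active, so 5235 − 3496 = 1739 control). The documents give neither p nor f. With p assumed at 1% to 5% and f at 5% to 50%, the result runs from 5235 × 0.01 × 0.05 = 2.6 to 5235 × 0.05 × 0.50 = 130.9. A range of about 3 to 131 is no estimate, and it does not remove cases still counted as SAEs or medically attended AEs.

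**The case against.** The strongest reply is that little is lost. Protocol 8.3.4.2 describes major anomalies as needing surgical or medical treatment, so one diagnosed at month 4 would very probably be medically attended and counted by arm in the 12-month endpoint. This stands. A reader might infer that late anomalies vanish from the analysis; the documents do not support that. Only an anomaly that is neither an SAE nor medically attended would be missing from both.

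A reader might also infer that affected infants remain classed as anomaly-free live births. No passage freezes the category at Day 43. The statistical methods column for these endpoints is redacted, and table layouts are in a separate document (SAP 10.2). For the same reason nothing can be said about how the SAE and medically attended AE tables are broken down.

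The opening text of SAP 5.4.1 lists infant summaries of neonatal AESIs with no time limit. That is true, but the endpoint table in the same section sets one. If later cases were meant to be included, the section needs to say so.

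Context also matters. Entry required a fetal anomaly scan without significant malformations (Protocol 5.1.1), vaccination came after the critical period for organogenesis (Protocol 4.3), and the 6-week window is protocol-specified and applies to both arms. These points argue against guessing a count and against alarm. They do not explain why anomalies the protocol chose to keep collecting lack a stated place in the AESI and pregnancy-outcome summaries.

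**Conclusion.** The concern holds as a gap between collection and endpoint wording. Neonatal AESIs and pregnancy outcomes are defined to 6 weeks; anomalies are sought and reported to month 12. Followed as written, the by-arm counts of congenital-anomaly AESIs (major external, internal, functional) omit those identified later, and no visible rule updates the live-birth category. What is at risk is their classification and count as anomalies. Those that are SAEs or medically attended remain in the 12-month primary infant safety endpoint.

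The part of follow-up outside the window is about 88%. The number of infants affected cannot be determined from the documents. The conclusion rests on reading the endpoint wording as the counting rule and on the unredacted text; a rule in the redacted column could narrow it.

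**What to change.** Keep the 6-week tables as they are. In SAP 5.4.1, add:
- a table by arm of all congenital anomalies identified from birth to Visit 5-NB, split into major external, major internal, major functional, and minor;
- a supportive pregnancy-outcome table in which live-birth anomaly status is re-derived from infant eCRF data through Visit 5-NB, including the physical-examination page for minor anomalies.

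State also which date (start, diagnosis or report) decides whether an anomaly falls in the 6-week table.

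The cost is a few lines of SAP text and two extra descriptive tables. No new data collection is needed.
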